#### **Participants**

All pre-college and university-level students from all European music academies will receive an invitation to complete a web-based questionnaire survey.

Pre-college will include third-year and fourth-year students (age: 18 and 19 years old). University-level will include students enrolled in the first, second and third year of the Bachelor degree course (age: between 19, 20 and 22, 23 years old), as well as students enrolled in the first, second and third year of Master degree course (age: between 22, 23 and 35 years old).

Inclusion criteria will be music students, men and women, aged 18 to 35 years old with a classical instrument as main subject (composers and conductors will be excluded).

Exclusion criteria will be composers and conductors, positive history for neurological, rheumatic, psychological disorders or emotional distress, as well as surgery of the upper limbs and/or the spine in the last year.

Blind recruitment will be used. The researcher will contact the student registries of the centres with an invitation e-mail that will be addressed to their student body.

The e-mail will contain information on the study, an information sheet and the link for the online survey. Once opened the link, students will be directed to the electronic consent form, which must be completed and signed before initiating any study procedure. Afterwards, once they have completed and signed the consent, they will be directed to the online-survey.

Questionnaire data and personal information provided through participant informed consents will be stored separately.

# Study procedure

The student registries of the ten centres will be used to recruit participants. The researcher will contact the relevant school offices with an invitation e-mail what will be addressed to their student body.

The e-mail will contain information on the study, an information sheet and the link for the online survey. Once opened the link, students will be directed to the electronic consent form, which must be completed and signed before initiating any study procedure. Afterwards, once they have completed and signed the consent, they will be directed to the online-survey.

Questionnaire data and personal information provided through participant informed consents will be stored separately.

The baseline online-survey will be conducted to investigate the prevalence of PRMDs of pre-college and university-level students of music. It aims to maximise sample size and to indirectly examine the influence of intensified music practice as expected at advancing levels of professional training.

Phase 1 will address secondary research questions 1, 2 and 5.

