#### Research questions and hypotheses

Primary research question:

What are the main factors associated with increased risk of PRMDs in music students undertaking professional training?

Secondary research questions/objectives:

- 1. What is the prevalence of musculoskeletal disorders among university-level students in comparison with pre-college students?
- 2. Monitor and characterise the impact of the transition between pre-college and university-level music training on the development of PRMDs.
- 3. (Are there any differences in the severity and symptoms associated with PRMDs among music student groups at different levels of music training?)
- 4. Monitor and characterise the time course of PRMD development

- 5. (Are there significant differences in PRMD incidence between university-level students and pre-college students?
- 6. During training, do music students develop any type of musculoskeletal disorder that doesn't affect their ability to play at the level to which they are accustomed to?
- 7. Characterise health related quality of life and outcomes in music students at different stages of professional training.

Considering the aims and the research questions of the programme, the following hypotheses are formulated:

H1: The development of PRMDs is associated with a multitude of risk factors (i.e. age, gender, number of hours of practice, previous history of injury, poor physical status, psychological stress, perfectionism, fatigue) among music students.

H2: There is a higher prevalence of PRMDs among university-level students in comparison with precollege students.

H3: There is a higher prevalence of PRMDs among university-level students in the early stages of their training (transition between university-level and pre-college).

H4: University-level students develop more PRMDs over the years of their training than pre-college students.

H5: During their training, music students of both levels develop MSK disorders that affect their ability to play at the level they are accustomed to.

H6: Health and quality of life among music students is progressively poorer over the years of training (from the last two years of pre-college to the last years of Master-level)

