# Methodology

#### Study Design

This prospective longitudinal cohort study will be conducted through the following three phases (Figure 1):

- (1) A baseline cross-sectional survey to characterise the study population and subgroups, and form the basis for the evaluation of associated factors and relationships with the development of PRMDs;
- (2) A 6-months follow-up survey, and
- (3) A 12-months follow-up survey.

[figure not shown]

Figure 1 Research planning chart including main features of the cohort study

The study protocol has been approved by the Research Ethics Panel of the Queen Margaret University, Edinburgh (REP 0177).

After the first baseline data collection (Phase 1), the cohort of students will be broken down into:

- Cohort 1: music students (both pre-college and university-level) who are free of pain, PRMDs and/or MSK problems at baseline data collection
- Cohort 2: music students (both pre-college and university-level) who aren't free of pain, PRMDs and/or MSK problems at baseline data collection

Afterwards, the two cohorts will be followed and invited for reassessment at 6 months (Phase 2) and 12 months (Phase 3).

The 6-months and 12-months follow-ups for the Cohort 1 will be essential to monitor and record the development of new incidents of invasive pain, PRMDs and/or MSK problems within a period of a year and to enable characterisation of the nature and time course of developing pain, PRMDs and/or MSK problems.

The analysis of the results will attempt to answer primary research question and secondary research question 3 and 4, addressing the lack of any similar type of data in the current literature.

Similarly, the follow-ups for the Cohort 2 will be important in order to characterise the impact and time course of changes in any pain, PRMD and/or MSK problem within a 12-month period.

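### Secondary question 2, on how entering university affects PRMD development, is assigned to the cross-sectional baseline survey and not to the follow-ups that record new cases

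*Protocol*

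**What the plan says.** Protocol, Research questions and hypotheses, gives secondary question 2 as: "Monitor and characterise the impact of the transition between pre-college and university-level music training on the development of PRMDs". The related hypothesis, H3, is about prevalence: "There is a higher prevalence of PRMDs among university-level students in the early stages of their training".

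Protocol, Study Design, describes Phase 1 as "A baseline cross-sectional survey to characterise the study population and subgroups". Study procedure adds its purpose, "The baseline online-survey will be conducted to investigate the prevalence of PRMDs of pre-college and university-level students of music", and then allocates the questions: "Phase 1 will address secondary research questions 1, 2 and 5". Just before that allocation it says that the baseline looks at the influence of advancing training only indirectly.

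Study Design calls the 6- and 12-month follow-ups of Cohort 1 (students free of pain, PRMDs and MSK problems at baseline) "essential to monitor and record the development of new incidents of invasive pain, PRMDs and/or MSK problems within a period of a year". The sentence that ties follow-up to research questions is "The analysis of the results will attempt to answer primary research question and secondary research question 3 and 4". It does not mention question 2.

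**The concern.** Question 2 is about change: what the transition does to the development of PRMDs. The survey assigned to it sees each student once. The follow-ups, which record new cases and which Study Design describes with the same term, *development*, are allocated to other questions.

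If the allocation is followed as written, the natural answer to question 2 is a comparison of prevalence between pre-college and early university students, in the form of H3. Such a difference could be reported as an effect of entering university when it partly or wholly reflects something else. It could also understate a real rise in onset, because prevalence soon after entry still carries much of what happened before it.

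**Working it through.** The documents state no figure on this point, so the check is mainly a comparison of texts.

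**1. Does the mismatch depend on the numbering?** Items 3 and 5 of the list open with a bracket and look like sub-items of the items before them. Both readings can be mapped to phases:

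| Phase sentence | Literal numbering | Bracketed items as sub-items |
|---|---|---|
| Phase 1: 1, 2, 5 | prevalence; transition; incidence comparison | prevalence; transition; quality of life |
| Follow-up: 3, 4 | severity by level; time course | time course with incidence comparison; disorders that do not affect playing |
| No phase named | 6 and 7 | none |

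The second reading is the more coherent: incidence goes to follow-up, and every question has a phase. Question 2 keeps its number and stays in Phase 1 under both.

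**2. What can Phase 1 show about the transition?**
- Nobody is observed on both sides of it.
- The question that divides the cohorts (The web-based survey) asks when the last bout occurred. It does not place first onset before or after university entry.
- Background/Rationale reports that 25% of university students in one study already had PRMDs before their degree course, so carry-over is expected.
- Prevalence depends on how long problems last as well as on how often they begin.
- On age, Participants says "Pre-college will include third-year and fourth-year students (age: 18 and 19 years old", while Bachelor students start at about 19. The levels overlap only at about 19, so age adjustment has little common ground to work on.
- Students who progress to university may differ from those who do not.

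**3. Would follow-up incidence alone settle it?** No. The following is an illustration with assumed inputs, not evidence about this study. Assume a 12-month onset of 25% (the level is borrowed from Background/Rationale, where it is not a 12-month figure), so the yearly rate is L = −ln(0.75) = 0.288. Assume that the rate doubles for the first 3 months after entry, that every fourth-year pre-college student enters at the next intake, and that the two pre-college years are equal in size. Baseline is k months after entry; the survey dates cannot be read, so k = 1 and k = 3 are both shown.

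With k = 3:
- First-year Bachelor: the doubled period is over, so onset is 1 − 0.75 = 25.0%.
- Third-year pre-college: 25.0%.
- Fourth-year pre-college: 9 months at L and 3 at 2L, so 1 − 0.75^(15/12) = 30.2%.
- Pooled pre-college: (25.0 + 30.2)/2 = 27.6%.

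First-year minus pooled pre-college is 25.0 − 27.6 = −2.6 points, the wrong direction. With the entrants taken out of the comparator it is 25.0 − 25.0 = 0: the rise is missed among first-years but not reversed, and it shows among the entrants (30.2%).

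With k = 1:
- First-year Bachelor: 1 − 0.75^(14/12) = 28.5%.
- Fourth-year pre-college: 1 − 0.75^(13/12) = 26.8%.
- Pooled pre-college: (25.0 + 26.8)/2 = 25.9%.

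The difference is then +2.6 points, or +3.5 with the entrants taken out. So the pooled contrast can change sign with survey timing alone. This shapes the fix.

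**The case against.** The strongest defence is that a cross-sectional proxy was intended and disclosed. Study procedure says that the baseline examines the influence of advancing training indirectly, and H3 puts the transition hypothesis in terms of prevalence, which a baseline survey can compare. Nothing says that Phase 1 *alone* will answer question 2. Data analysis plans longitudinal comparisons from both follow-ups, and Figure 1, which is not shown, may carry a fuller mapping. If bracketed item 3 is a sub-item of question 2, its comparison of severity between levels suits Phase 1.

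Much of this stands, and it limits the point. It does not remove it. H3 and the severity sub-item fit Phase 1, but question 2 itself asks about impact on development. The longitudinal comparisons in Data analysis are general: training level is not among the variables listed for the incidence analysis, and the stated comparison of pre-college with university students covers gender, study, prevalence rate and practice hours.

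Three stronger readings are tempting and not supported:
- *The study cannot answer question 2.* The documents plan follow-up of both cohorts at 6 and 12 months and do not exclude its use here.
- *The protocol contradicts its own Background.* That passage concerns the direction of effect when factor and outcome are measured together, with anxiety as its example. Year of study is set by enrolment, so the argument carries over only in part, through selective progression.
- *The incidence comparison is also misassigned.* That holds only under the literal numbering.

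**Conclusion.** The point holds as a mismatch between a secondary question and the phase assigned to it. It rests on the wording of three sections and does not depend on how the list is numbered. It does not touch the primary question, and no data collection is shown to be missing.

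Its size cannot be stated. A reader might want a figure for how far a prevalence contrast would depart from the true change in onset, but onset rate, symptom duration and survey timing would all have to be assumed, so none is offered as evidence. The illustration above supports only a caution about the remedy: Cohort 1 leaves out students affected between entry and baseline, so follow-up incidence is not a stand-alone test either. Confidence is moderate, because Figure 1 could not be read.

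**What to change.** - Assign question 2 to Phases 2 and 3 as well as Phase 1.
- Record training level at each wave, if this is not already planned.
- Report new PRMD incidents in Cohort 1 over 6 and 12 months descriptively, with 95% confidence intervals, by year of study at baseline (two pre-college, three Bachelor and three Master years).
- Show students who enter university during follow-up separately, and do not leave them in the pre-college comparator.
- Keep the Phase 1 contrast for H2 and H3, call it prevalence only, and present it beside the follow-up results.
- Correct the numbering in Research questions and hypotheses so that the allocations in Study Design and Study procedure match it.

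The cost is wording and, at most, one item per wave; no new survey is needed. Year groups will be small. As an assumption-based guide, with eight equal groups, 25% onset and no attrition, the half-width per group is 1.96 × √(0.1875 × 8/N): 17.0, 12.0 or 8.5 points for a Cohort 1 of N = 200, 400 or 800. Age and selection differences between years remain, and a short-lived rise just after entry can still be missed. The result is therefore descriptive, to be read together with Phase 1.

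### As printed, the secondary question on PRMD incidence by training level is assigned to the cross-sectional baseline survey, which cannot measure incidence, and not to the follow-ups that can

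*Protocol*

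**What the plan says.** Research questions and hypotheses prints seven numbered secondary items. Item 5 reads "Are there significant differences in PRMD incidence between university-level students and pre-college students". Items 3 and 5 are the only two that open with a bracket.

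Two sentences link the secondary questions to phases by number:

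- Study procedure, on the baseline survey: "Phase 1 will address secondary research questions 1, 2 and 5".
- Study Design, directly after describing the Cohort 1 follow-ups: "The analysis of the results will attempt to answer primary research question and secondary research question 3 and 4".

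Study Design defines Phase 1 as a cross-sectional baseline survey, and Study procedure gives its purpose as the prevalence of PRMDs at the two levels. New cases are the business of the Cohort 1 follow-ups, which are there to "monitor and record the development of new incidents of invasive pain, PRMDs and/or MSK problems within a period of a year".

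Under Data analysis, the one stated comparison between pre-college and university-level students includes the prevalence rate but not incidence. The variables to be related to incidence are gender, instrument group, age, years of playing, hours of practice and questionnaire scores. Data management repeats that list. Training level is in neither.

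**The concern.** Incidence needs students who are free of the condition at a starting point and are then watched for new onsets. One survey at one time cannot supply that. Followed as printed, the protocol would send its incidence question to the phase that cannot answer it and leave it out of the phase that can.

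Hypothesis H4, that university-level students develop more PRMDs than pre-college students, depends on this question. A baseline prevalence contrast is not a substitute. Current and 12-month prevalence depend on how long problems last as well as on how often they start. Ever/never prevalence depends on years at risk, and by the Participants section the university-level students are older. The protocol's own Background makes a related point when it rejects cross-sectional studies as a basis for research on risk factors.

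**Working it through.** No sample size, power or error-rate figure is involved, so there is no formula to reproduce. The check sets the printed list beside the two assignment sentences.

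**Step 1: the list as printed**

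| Printed item | Subject | Phase in the readable text |
|---|---|---|
| 1 | Prevalence by level | Phase 1 |
| 2 | Effect of the transition to university level | Phase 1 |
| 3 (opens with a bracket) | Severity and symptoms by level | Follow-up |
| 4 | Time course of PRMD development | Follow-up |
| 5 (opens with a bracket) | PRMD incidence by level | Phase 1 |
| 6 | MSK disorders that leave playing ability intact | None |
| 7 | Health-related quality of life by stage | None |

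Phase 1 takes {1, 2, 5} and follow-up takes {3, 4}. Together they cover 3 + 2 = 5 of 7 items, leaving 7 − 5 = 2 without a phase. Those two are item 6, which opens "During training, do music students develop any type of musculoskeletal disorder that", and item 7, "Characterise health related quality of life and outcomes in music students at different stages of professional training".

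**Step 2: can Phase 1 answer item 5?** The screening question in The web-based survey asks when the last bout occurred, with six answers running from a current problem (up to one month) to never. This gives current, 12-month and ever/never prevalence. It asks about pain or MSK problems in general, not PRMDs, and does not separate a first onset from a recurrence. It cannot give new PRMD cases among students at risk.

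**Step 3: does other text move item 5 to follow-up?** Study Design records new cases in Cohort 1, and Data analysis has an incidence analysis. Neither names the comparison by level: the first is tied to other questions, and the second omits training level from its variables.

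**Step 4: could the numbering be stale?** Suppose the two bracketed items are sub-questions, item 3 belonging to item 2 and item 5 to item 4. Then 7 − 2 = 5 questions remain:

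| Renumbered | Subject | Phase under the two sentences |
|---|---|---|
| 1 | Prevalence by level | Phase 1 |
| 2 | Transition, with severity | Phase 1 |
| 3 | Time course, with incidence | Follow-up |
| 4 | MSK disorders that leave playing intact | Follow-up |
| 5 | Health-related quality of life | Phase 1 |

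The two sentences now use each number once, cover all five questions, and put incidence under follow-up. On this reading the 5 in Study procedure stands for quality of life. The fit is good but does not prove the case. Item 2 also speaks of the development of PRMDs and still sits in a cross-sectional phase, although Study procedure does say the baseline survey will look at the effect of intensified practice only indirectly.

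**The case against.** The strongest reply is that this is one wrong cross-reference and not a wrong plan. The bracket pattern suggests an older five-question list, and it cannot be shown whether the extra numbers come from the authors or from the reading of the PDF. Much of this stands. It lowers confidence and means that replacement numbers cannot be written from this text alone. It does not remove the point, because the text as it reads gives an instruction that cannot be carried out, and the omission of training level from the incidence variables does not depend on the numbering.

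A second reply is that analysis detail may sit in a statistical analysis plan that is not shown. That would excuse silence. Here the protocol names its incidence variables and leaves out the one that a secondary question requires.

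Four stronger readings are tempting and should not be drawn:

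- *That the investigators mean to pass off prevalence as incidence.* Study Design places new cases at follow-up, and Data analysis keeps the prevalence comparison separate from the incidence analysis.
- *That items 6 and 7 have no phase at all.* Figure 1, the planning chart, is not shown and may assign them. The statement holds for the readable text only.
- *That item 3 on severity is also misplaced, because the pain and disability measures belong to baseline.* The Abstract says the survey is completed on all three occasions, so severity can be compared at follow-up.
- *That the distortion can be given a number.* The protocol gives no incidence or duration by level, so any ratio of prevalence to incidence would rest wholly on assumed inputs.

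**Conclusion.** The point holds, with moderate confidence. As printed, the incidence-by-level question is assigned to a survey that cannot answer it and is absent from the follow-up analysis that can. The size is a count: one of seven secondary questions is in an unsuitable phase and two have no phase in the readable text. The effect on any estimate cannot be sized from the protocol. The harm is limited, since the primary question is correctly placed, the follow-ups that yield new cases are already planned, and no data are lost. The conclusion rests on the numbers as they appear in this text; if the source file shows items 3 and 5 as unnumbered sub-questions, the phase assignment resolves itself and only the missing training-level variable remains. It should be fixed, because H4 depends on it and correction is cheap.

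**What to change.** 1. Check the numbering in Research questions and hypotheses, Study Design and Study procedure against the source file, and reconcile the three. Refer to each question by its text so that later renumbering cannot break the link. Place the comparison of PRMD incidence by level under the 6- and 12-month follow-ups of Cohort 1, and name a phase for items 6 and 7 if Figure 1 does not. Do not simply delete the 5 from Study procedure, since it may stand for the quality-of-life question.
2. In Data analysis, add baseline training level to the incidence variables, and report 12-month PRMD incidence in Cohort 1 by level with a 95% CI.

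The cost is a few text changes and one added comparison, using a variable that the planned comparison by level already needs. No new data are required. The downside is that the incidence comparison rests on fewer students, only those free of problems at baseline and then followed, and is reported later than a baseline result would be.
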